16.9.3.2 For Passive Access to Original Documents/Original Data via Live Image Transmission

The following controls will be applied for remote data review by video call/conferencing:

- The video call/conference may only occur using a Syneos Health approved information and communication technology.
- Video review of documentation only is permitted.
- No recording of the interaction is permitted.
- No document upload is permitted.
- No Document storage is permitted.

- Usage must comply with applicable local regulations/regulatory guidance.
- During remote data review by video call/conferencing care will be taken to avoid inadvertent viewing of individuals who should not be part of the interaction.

16.9.3.3 Passing on Redacted Copies of Original Documents and Documents with Original Data

Note: In Germany, the sending of redacted source data is generally not permissible as a method for the remote review of data; however, single redacted documents may be used at times to confirm an individual data-point.

The following controls will be applied during for passing on redacted copies of original documents:

- Process must be allowed by local regulations and in compliance with applicable regulatory guidance
- Principal Investigator to document the delegation of creation of Pseudonymized Certified Copies of the source documents on the Study Personnel Signature and Delegation Form
- Site staff who will provide source documents to Monitor for remote data review will be trained on the role, responsibility, and process for providing pseudonymized Certified Copies of source documents to support remote review of data
- Certified Copies of all required original source documents will be prepared

Certified Copy: A copy (irrespective of the type of media used) of the original record that has been verified (i.e., by a dated signature or by generation through a validated process) to have the same information, including data that describe the context, content, and structure, as the original. (International Council for Harmonization (ICH) Guideline for Good Clinical Practice (GCP) Revision 2).

Note: A copy is certified by signing and dating on the first page with a statement “certified copy” and adding a note on the first page that the certified copy package consists of # pages. Each page must be numbered so that, in total, the pages match the full # of pages documented on the first page of the package.

- All subject direct identifiers (e.g. name, social security/national identification number, medical record number, initials, full date of birth, home address etc.) will be redacted/obscured (i.e. pseudonymized) on the copies to protect subject confidentiality and personal data.
- A quality check of the redacted Certified Copies will be performed by a second site staff member to confirm all subject directly identifiable information has been redacted, the correct subject identification code added and that the copies are legible.
 - The quality check will be documented by the second site staff member’s initials, dating of the first page of the package and addition of the statement “QC’d/Checked”
- A transmittal form will be completed each time Pseudonymized Certified Copies of source documents are sent.

- The prepared source document package, including transmittal form, will be provided by one of the following methods:
 - Overnight Courier
 - Secure Fax Transmission
 - Scanned images via secure email (encrypted email or password protected email attachment. If the latter, the password will be provided to Monitor via telephone)
 - A secure platform for document exchange
- A set of the prepared source document package, including transmittal form, will be retained in the Investigator's Site File. Note: These documents will not be retained in Germany.

This Phase 2 multi-center, open-label study will evaluate the safety, efficacy and pharmacodynamics of IMG-7289, an irreversible inhibitor of the enzyme lysine-specific demethylase 1 (LSD1) when administered orally once daily in patients with essential thrombocythemia (ET). ET is an indolent hematologic cancer characterized by reduced quality of life, thrombocytosis, elevated cytokines, and increased rates of thrombosis and bleeding that can evolve to myelofibrosis and/or acute myeloid leukemia. LSD1 is an enzyme that regulates the maturation of megakaryocytes from progenitor cells, as well as the function of mature megakaryocytes. In ET, acquired mutations in hematopoietic stem cells cause JAK/STAT activation, which results in an over-abundance of activated megakaryocytes that in turn produce an excess of platelets, growth factors, and inflammatory cytokines.

2. Study Objectives

The following primary and exploratory objectives will be evaluated in patients with ET treated with IMG-7289:

2.1 Primary Objectives

- Safety and tolerability.
- Reduction of platelet counts to ≤ 400 k/ μ L ($400 \times 10^9/L$) in the absence of new thromboembolic events.

CCI

This document is confidential.

Statistical Analysis Plan

Sponsor: Imago BioSciences, Inc; Protocol No.: IMG-7289-CTP-201

3. Study Design

This is a Phase 2 multi-center, open-label study evaluating the safety, efficacy, and pharmacodynamics of IMG-7289 administered orally once daily in patients with ET.

The therapeutic goal for the treatment of ET is to inhibit the activity of LSD1 in hematopoietic cells for only a fraction of the 24-hour dosing cycle, sufficient to reduce the production of platelets, whose over-production characterizes this condition. Considerations leading to the choice of a safe starting dose include chronic toxicology studies in conjunction with the clinical experience of the patients who have received IMG-7289 to date. Using all of the information available in conjunction with the therapeutic goal for the treatment of ET, an IMG-7289 starting dose of 0.6 mg/kg QD has been selected.

To ensure patient safety, a Safety Advisory Board (SAB) will perform reviews at least quarterly of safety parameters and pharmacodynamic markers to draw conclusions around the safety and pharmacodynamic effect of IMG-7289. The SAB will also review patient dose titrations and may recommend adjustments.

This study consists of 2 treatment periods: The Initial Treatment Period (ITP), followed by the Additional Treatment Period (ATP). In the ITP, patients will be treated daily for 169 days. In the ATP, which is iterative, treatment may continue for an additional 169 days in those patients deriving clinical benefit (defined as not meeting "progressive disease" criteria as per Appendix 16.5 in the Protocol) and safely tolerating IMG-7289; as determined by the Principal Investigator (PI).

All patients will undergo follow-up period visits, including an End-of-Treatment (EoT) visit on the day of last dose or as soon as possible thereafter, a pre-End-of-Study (EoS) visit approximately 7 days post last dose, and an End-of-Study (EoS) visit approximately 14 days post last dose. Patients that do not enter the ATP, or discontinue early, will undergo follow-up beginning with an EoT visit.

Patients will be followed closely throughout the study for both adverse events (AEs) and signs of toxicity by frequent monitoring of clinical signs and symptoms as well as safety laboratory parameters. Efficacy and pharmacodynamic effects will be closely monitored by frequent hematology assessments of peripheral blood, and requisite bone marrow aspirates and biopsies. Throughout dosing, transfusions may be administered if needed in accordance with standard institutional guidelines.

3.1 Initial Treatment Period (ITP)

Through the use of dose titration, the dose of IMG-7289 will be adjusted in each patient to that dose that provides sufficient exposure to safely inhibit thrombopoiesis for a fraction of the dosing cycle (designated as the D_{pi}). Treatment will begin on Day 1 at the IMG-7289 D_s of 0.6 mg/kg QD for all patients, with dose-titration contingent on the comparison of hematology values from the prior visit. **Up-titrations** may begin on ITP Day 28 and occur no more frequently than every 4 weeks from the previous up- or down-titration. **Down-titrations** can be made at any time in the best interest of the patient. Up-titrations will be made in increments of 0.2 mg/kg/d, and down-titrations in decrements of 0.1 or 0.15 mg/kg/d, as summarized in tabular form in Table 1.

CCI

This document is confidential.

Statistical Analysis Plan

Sponsor: Imago BioSciences, Inc; Protocol No.: IMG-7289-CTP-201

CCI

During the ITP, patients will initially return for study assessments every other week (bi-weekly) for the first 12 weeks (ITP Days 15, 29, 43, 57, 71 and 85) and then monthly for 12 weeks (ITP Days 113, 141 and 169). It is anticipated that by Week 12 (Day 85) the majority of patients will have achieved a stable dose. For safety purposes, bi-weekly visits may continue at the PI's discretion post Day 85 if necessary. On Day 169 bone marrow sampling is also required. Additionally, at the Day 169 visit a 'qualification' assessment will be made to determine whether the patient is deriving clinical benefit and safely tolerating IMG-7289. For the patients who qualify for entry into the ATP, transition should occur without interruption in dosing. Patients not deriving clinical benefit will discontinue IMG-7289 and undergo End of Treatment (EoT), pre-End of Study (pre-EoS) and End of Study (EoS) visits.

3.2 Additional Treatment Period (ATP) for Qualifying Patients Only

In the ATP, treatment may continue for an additional 169 days in those patients deriving clinical benefit, as determined by the PI. For the purposes of clarity and efficiency, rather than continuing to present chronological days/weeks, visits are presented as 'ATP Day 1', followed by, 'ATP Days 29, 57, 85', etc. Qualifying patients will 're-start' IMG-7289 on ATP Day 1, with dose titration continuing as per the Titration and Re-challenge Rules (Table 1); there should be no interruption in dosing (Day 169 = Day 1 of the next ATP). Additional dose-titration may occur in consultation with the Medical Monitor.

Qualifying patients will return for study assessments monthly (ATP Days 1, 29, 57, 85, 113, 141 and 169). It is anticipated that patients continuing in the ATP will have already achieved a stable dose, with every other week visits no longer necessary. For safety purposes, every other week visits may continue at the

This document is confidential.

Statistical Analysis Plan

Sponsor: Imago BioSciences, Inc; Protocol No.: IMG-7289-CTP-201

PI's discretion, if necessary. On Day 169 of every other ATP (i.e., ATP 2, 4, etc.), the equivalent of yearly, patients will undergo bone marrow sampling. At the Day 169 visit, a 'qualification' assessment will be made to determine whether the patient is continuing to derive clinical benefit. Such patients thereby qualify for re-entry into the ATP, which is iterative; patients may continue to receive IMG-7289 for as long as they continue to qualify. Patients not deriving clinical benefit will discontinue IMG-7289 and undergo EoT, pre-EoS, and EoS visits.

CCI

This document is confidential.

Statistical Analysis Plan

Sponsor: Imago BioSciences, Inc; Protocol No.: IMG-7289-CTP-201

CCI

[figure not shown]

This document is confidential.

Statistical Analysis Plan

Sponsor: Imago BioSciences, Inc; Protocol No.: IMG-7289-CTP-201

08HHB8

CCI

[figure not shown]
This document is confidential.

Statistical Analysis Plan

Sponsor: Imago BioSciences, Inc; Protocol No.: IMG-7289-CTP-201

08HHB8

CCI

[figure not shown]

This document is confidential.

Statistical Analysis Plan

Sponsor: Imago BioSciences, Inc; Protocol No.: IMG-7289-CTP-201

08HHB8

[figure not shown]
CCI

Statistical Analysis Plan

Sponsor: Imago BioSciences, Inc; Protocol No.: IMG-7289-CTP-201

08HHB8

CCI

This document is confidential.

Statistical Analysis Plan

Sponsor: Imago BioSciences, Inc; Protocol No.: IMG-7289-CTP-201

5. Analysis Populations

The following subject populations (i.e., analysis sets) will be evaluated and used for presentation of the data.

5.1 Safety Population

The Safety Population will include all subjects who are enrolled in the study and receive at least 1 dose of study medication. Subjects will be analyzed according to treatment received in the study. The Safety Population will be used for all analyses of demographics, baseline characteristics, safety endpoints, and for subject disposition at the end of treatment. The Safety Population will be used for all data listings, with the exception of subject disposition at the end of study.

5.2 Modified Intent-to-Treat (mITT) Population

The mITT Population will include all subjects who are enrolled in the study, receive at least 1 dose of study medication, and who have a non-missing baseline and at least 1 non-missing post-baseline efficacy assessment. Subjects will be analyzed according to treatment received in the study. The mITT Population will be used for all analyses of efficacy and pharmacodynamic endpoints.

CCI

This document is confidential.

Statistical Analysis Plan

Sponsor: Imago BioSciences, Inc; Protocol No.: IMG-7289-CTP-201

6. Statistical Methodology

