12 ANALYSIS AND STATISTICAL CONSIDERATIONS

12.1 General Considerations

Detailed methodology for summary and statistical analyses of the data collected in this trial will be documented in a Statistical Analysis Plan (SAP). This document may modify the plans outlined in the protocol; however, any major modifications of the primary endpoints definition and/or its analysis will also be reflected in a protocol amendment. Additional statistical analyses other than those described in this section may be performed if deemed appropriate and included in the SAP.

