6.1.4 Determination of Sample Size

This study is designed to make an assessment of the safety, tolerability, and efficacy of IMG-7289 for the treatment of essential thrombocythemia. This is a single-arm trial with a primary endpoint that is a proportion variable (proportion of subjects who achieve a reduction in the platelet count to ≤ 400 k/ μ L in the absence of new thromboembolic events). The test of significance is a 1-sided test at the $\alpha=0.025$ level of significance (equivalent to a 2-sided test at the $\alpha=0.05$ level of significance) CCI

CCI

with a sample size of 21 subjects, there is an 80% probability that the study will be successful (where “success” is defined as rejecting the null hypothesis that the true rate is as low as 5%). If the sample size is increased to 30 subjects, the probability of study success is 90%.

This document is confidential.

Statistical Analysis Plan

Sponsor: Imago BioSciences, Inc; Protocol No.: IMG-7289-CTP-201

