6.3 Efficacy Analysis

All efficacy analyses will be performed using the mITT Population. CCI [Redacted] Summaries will be presented overall for the ITP and ATP, unless otherwise noted below.

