6.3.1 Primary Efficacy Analysis

The primary efficacy objective for this study is to evaluate the reduction of platelet counts to ≤ 400 k/ μ L ($400 \times 10^9/L$) in the absence of new thromboembolic events. The reduction of platelet counts will be evaluated and assessed based on local laboratory measurements of platelet counts from Day 1 to each visit where platelets are measured CCI [Redacted]

The primary efficacy endpoint is the proportion of subjects who achieve a reduction of platelet counts to ≤ 400 k/ μ L ($400 \times 10^9/L$) in the absence of new thromboembolic events. This endpoint will be analyzed using an exact 1-sample binomial test. The proportions and corresponding 95% confidence intervals (CIs) based on the Clopper-Pearson method will be presented for each post-baseline study visit on the mITT Population. 2-sided p -values will be calculated for the Day 169 visit to test the null hypothesis assuming that the test statistic follows an exact binomial distribution.

The null hypothesis tested for the primary efficacy endpoint is that the true response rate is 5%, where the response rate is defined as the proportion of subjects who achieve a reduction of platelet counts to ≤ 400 k/ μ L ($400 \times 10^9/L$) in the absence of new thromboembolic events. The corresponding alternative hypothesis is that the true response rate is not 5%. The primary efficacy endpoint will be achieved if the null hypothesis is rejected at the 0.05 alpha level in favor of a higher ($> 5\%$) response rate.

CCI [Redacted]

CCI [Redacted]

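### The primary exact test is run on mITT, which drops dosed patients with no post-baseline efficacy assessment; against an all-dosed, missing-equals-non-response analysis this can only raise the response rate, probably by little

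*SAP*

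**What the plan says.** SAP 5.2 admits to mITT the enrolled, dosed subjects "who have a non-missing baseline and at least 1 non-missing post-baseline efficacy assessment". SAP 6.3 states: "All efficacy analyses will be performed using the mITT Population". SAP 6.3.1 repeats this for the primary endpoint: response proportions with Clopper-Pearson intervals "will be presented for each post-baseline study visit on the mITT Population". It adds an exact binomial p-value at Day 169 against a fixed null rate of 5%.

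An all-dosed set is already defined in SAP 5.1: "The Safety Population will include all subjects who are enrolled in the study and receive at least 1 dose of study medication". Its visible uses are demographics, baseline, safety, disposition at end of treatment and listings ("The Safety Population will be used for all data listings", apart from end-of-study disposition). The visible text gives it no efficacy role.

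The visible text does not say how a patient without a Day 169 platelet count enters the Day 169 proportion. Parts of SAP 5.2, 6.1.2, 6.3 and 6.3.1 are blacked out.

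**The concern.** Membership of the primary analysis set depends on what happens after dosing. The post-baseline clause can remove only patients for whom response was never observed, so as a selection it runs in one direction. The trial has no control arm in which the same exclusions would occur, and the comparison is with a fixed 5%. Nothing in the design offsets the shift. Early death, withdrawal of consent or loss may also be related to treatment.

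At stake is mainly the reported response rate, which would describe slightly fewer than all treated patients. In a narrow borderline case the test decision could also change.

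**Working it through.** **Inputs.** Null rate 5% (SAP 6.3.1). One-sided level 0.025 (SAP 6.1.4: "The test of significance is a 1-sided test at the" 0.025 level, described there as equivalent to two-sided 0.05). About 60 patients enrolled and treated (Protocol 6.2). The number of dosed patients with no post-baseline efficacy assessment, k, is not given, so a range is shown as an assumption.

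**1. The plan's own figure.** SAP 6.1.4 states that "with a sample size of 21 subjects, there is an 80% probability that the study will be successful", and 90% with 30. The planning response rate is redacted, so I solved for it. With the exact one-sided 0.025 rule, 21 patients need at least 4 responders and power is 80% at a rate of 24.7%. Thirty patients need at least 5, and power is 90% at 24.9%. At an assumed 25% the powers are 80.8% and 90.2%. Both stated figures reproduce, and 25% is used below as the back-solved planning rate.

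**2. Direction.** With x responders among 60 dosed, the all-dosed rate with missing counted as non-response is x/60, and the mITT rate is x/(60 − k). The second exceeds the first whenever x > 0 and k > 0. If x = 0, both are 0%.

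**3. Size of the shift** (rate, with Clopper-Pearson 95% limits):

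| Responders | k = 0 | k = 1 | k = 3 |
|---|---|---|---|
| 30 | 50.0% (36.8 to 63.2) | 50.8% (37.5 to 64.1) | 52.6% (39.0 to 66.0) |
| 15 | 25.0% (14.7 to 37.9) | 25.4% (15.0 to 38.4) | 26.3% (15.5 to 39.7) |
| 0 | 0% (upper 5.96) | 0% (upper 6.06) | 0% (upper 6.27) |

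**4. Test decision.** P(X ≥ 7) at a 5% rate is 0.0297 for n = 60, 0.0274 for n = 59, 0.0252 for n = 58 and 0.0231 for n = 57. P(X ≥ 8) for n = 60 is 0.0098. The smallest passing count is therefore 8 at n = 58 to 60, and 7 at n = 46 to 57 (k = 3 to 14). Over that range the decision changes only with exactly 7 responders and at least 3 exclusions.

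SAP 6.3.1 calls for a two-sided p-value, so the convention matters here. Doubling the one-sided value gives 0.0594 for 7/60, 0.0504 for 7/58 and 0.0462 for 7/57, which is the same change at k = 3. Summing the probabilities of outcomes no more likely than the one observed gives 0.0297 for 7/60, which already passes, and 0.0520 for 6/54, which still fails. Under that convention nothing changes through k = 6.

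**5. Chance of a changed decision (one-sided rule).** Suppose each dosed patient has probability q of being an excluded non-responder and r of responding. Sum over k from 3 to 12 of P(K = k) × P(X = 7), with K ~ Binomial(60, q) and X ~ Binomial(60 − k, r/(1 − q)). Both q values are assumptions.

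| | r = 25% | r = 20% | r = 15% |
|---|---|---|---|
| q = 2% | 0.09% | 0.53% | 1.5% |
| q = 5% | 0.39% | 2.4% | 7.3% |

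**6. One-sided error when the true rate over all dosed patients is 5%.** For a fixed number of exclusions, with total responders Binomial(60, 0.05), it is 0.0098 for k = 0 to 2 (bar 8). It is 0.0297 from k = 3 (bar 7, checked to k = 7). Averaged over a random number of exclusions, using the model in step 5 with r = 5%, it is 0.0118 at q = 2% and 0.0204 at q = 5%.

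**The case against.** **The comparator.** The upward shift presumes that these patients would otherwise count as non-responders. The p-value is for Day 169, and a patient with no post-baseline assessment has no Day 169 count. If the proportion uses observed counts only, that patient is out of the denominator whether the set is mITT or all dosed, and the clause makes no difference. This objection stands. The finding is conditional on the comparison being all dosed with missing as non-response.

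**Redaction.** A further population or an all-dosed sensitivity analysis may be planned in blacked-out text. That also stands, and no claim is made that one is missing. However, a missing-data rule applied within mITT acts only on its members and cannot restore excluded patients.

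**Reach.** Any one post-baseline efficacy assessment is enough for inclusion. Hematology is scheduled at every visit and at EoT, pre-EoS and EoS (Protocol Synopsis), and early discontinuers enter that follow-up (Protocol 5.1). Exclusion needs death, withdrawal or loss before all of these. The by-subject listings cover all dosed patients, so a reader could recompute the rate. This keeps the point minor, although the planned primary result would still use the smaller denominator.

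**Validity of the test.** For the rate among mITT patients, the exact test keeps its level. The 0.0297 in step 6 arises only when the null rate is defined over all dosed patients.

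A reader might infer that the headline rate will be materially inflated, or that the test is not controlled at its level. The schedule and the figures do not support the first, and the second depends on at least 3 such losses and on that definition of the null.

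**Conclusion.** The point holds as an optional improvement. Against an all-dosed analysis that treats these patients as non-responders, the mITT clause can only raise the estimate or, with no responders, leave it at 0%. At 60 dosed, one exclusion adds about 0.4 points to a 25% rate and 0.8 points to a 50% rate, well inside intervals more than 20 points wide.

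The decision is rarely affected. Under the one-sided rule it needs exactly 7 responders and at least 3 exclusions. At the back-solved 25% rate, P(8 or more of 60) is 99.1% before any exclusion.

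That exclusions will be few is a judgement from the visit schedule, since the documents give no expected number. The conclusion covers only the post-baseline clause. It does not extend to the missing-baseline clause, or to mITT patients whose Day 169 count is missing. It would be tempting to read the clause as dropping everyone without a Day 169 count, but SAP 5.2 does not say that.

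**What to change.** In SAP 5.2, 6.3 and 6.3.1, run the primary efficacy test on all patients who received at least one dose, which is the existing Safety Population. State that those with no post-baseline efficacy assessment count as non-responders, so that they stay in the Day 169 denominator. Without that statement, changing the set might alter nothing. Keep mITT as a sensitivity analysis and, if the redacted text does not already provide for it, report how many dosed patients mITT excludes and why.

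The cost is rewording in three SAP sections, with no new data, and possibly a slightly lower reported rate. If nobody is excluded, the two sets do not differ on this clause. Protocol 12.1 says that "any major modifications of the primary endpoints definition and/or its analysis will also be reflected in a protocol amendment", so a conforming amendment is needed if the sponsor considers the change major. SAP 6.8, which declares no changes from the protocol's methods, should then be checked for consistency.
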